#### 5.4.8. Management of hyperlipidemia and hyperglycemia

Treatment of hyperlipidemia and hyperglycemia should consider the pre-treatment status and dietary habits. Blood tests to monitor hyperlipidemia must be taken in the fasting state. Grade  $\geq 2$  hypercholesterolemia or hypertriglyceridemia should be treated with a 3-hydroxy-3-methyl-glutaryl (HMG)-CoA reductase inhibitor (e.g. atorvastatin, pravastatin) or appropriate lipid-lowering medication, in addition to diet. Patients should be monitored clinically and through serum biochemistry for the development of rhabdomyolysis and other adverse events as required in the product label/data sheets for HMG-CoA reductase inhibitors.

[figure not shown]
#### 5.4.9. Management of non-infectious pneumonitis

Non-infectious pneumonitis is a class effect of rapamycin derivatives. Cases of non-infectious pneumonitis (including interstitial lung disease) have also been described. A diagnosis of non-infectious pneumonitis should be considered in patients presenting with non-specific respiratory signs and symptoms such as hypoxia, pleural effusion, cough, or dyspnea and in whom infectious, neoplastic, or other non-medicinal causes have been excluded by means of appropriate investigations. Patients should be advised to report promptly any new or worsening respiratory symptoms. For patients who develop radiological changes suggestive of non-infectious pneumonitis, and have few or no symptoms, may continue sirolimus with dose alteration. Dose modifications and retreatment are described in table below:

Worst Grade Pneumonitis	Required Investigations	Management of Pneumonitis	Sirolimus Dose Adjustment
Grade 1	CT scans with lung windows and pulmonary function testing including: spirometry, DLCO, and room air O 2 saturation at rest. Repeat chest x-ray/CT scan every 2 cycles until return to baseline.	No specific therapy is required	No change in dose.
Grade 2	CT scan with lung windows and pulmonary function testing including: spirometry, DLCO, and room air O 2 saturation at rest. Repeat each subsequent cycle until return to baseline. Consider bronchoscopy *	Symptomatic only. Prescribe corticosteroids if cough is troublesome.	Reduce sirolimus dose to 50% lower dose than previously administered until recovery to ≤ Grade 1. Sirolimus may also be interrupted if symptoms are troublesome. Patients will be withdrawn from protocol treatment if they fail to recover to ≤ Grade 1 within 3 weeks.
Grade 3	CT scan with lung windows and pulmonary function testing including: spirometry, DLCO, and room air O 2 saturation at rest; Repeat each subsequent cycle until return to baseline. Bronchoscopy is recommended *	Prescribe corticosteroids if infective origin is ruled out. Taper as medically indicated.	Hold treatment until recovery to ≤ Grade 1. May restart protocol treatment within 2 weeks at a reduced dose if evidence of clinical benefit. Patients will be withdrawn from the study if they fail to recover to ≤ Grade 1 within 2 weeks.
Grade 4	CT scan with lung windows and required pulmonary function testing includes: spirometry, DLCO, and room air O 2 saturation at rest. Repeat each subsequent cycle until return to baseline. Bronchoscopy is recommended *.	Prescribe corticosteroids if infective origin is ruled out. Taper as medically indicated.	Discontinue treatment.

[figure not shown]
\*A bronchoscopy with biopsy and/or bronchoalveolar lavage should be considered (grade 2) or is recommended (grade 3 or 4). For any grade infection should be ruled out prior to prescribing corticosteroids.

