### 5.2. Criteria to start subsequent cycles

(Refer to section 6 for dose modifications)

A cycle may be repeated every 28 days if the patient has at least stable disease, has again met the ANC, platelet, hepatic, and renal function defined in Section 3.1, and has not met one of the off protocol therapy or off study criteria in Section 5.6 and 5.8. Up to 21 days (to day 49) will be allowed between cycles for recovery without modifying drugs on subsequent cycles if toxicity did not meet criteria requiring dose modification.

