## 5.6. Duration of Follow Up

Patients will be followed for adverse event(s) until 30 days after last treatment or until resolution or stabilization of the adverse event (whichever comes last). Patients who are removed from protocol therapy for a reason other than disease progression, should be followed up every 6 months by imaging to monitor disease status. Every effort should be made to collect information regarding disease status until the start of new anti-cancer therapy, disease progression, or death. Once a patient experiences confirmed disease progression or starts a new anti-cancer therapy, the patient should be contacted by telephone every 6 months to assess for survival status until death or withdrawal of consent or end of study, whichever occurs first.

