## 5.7. Criteria for Removal from Study

Patients will be removed from study when any of the criteria listed below applies. The reason for study removal and the date the patient was removed must be documented in the Case Report Form including death or lost to follow up.

- Patient or guardian withdrawal of consent. Reasons must be noted on the patient's record.
- Death

- Lost to follow up
- Enrollment onto another SARC treatment study or SARC long term follow up study.

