## 6. DOSING DELAYS / DOSE MODIFICATIONS

Patients who experience a toxicity requiring dose modification attributed to selumetinib and sirolimus but in the opinion of the investigator have benefited from the prior treatment cycle (decrease in size or stabilization of tumor or decrease in tumor related symptoms such as pain) may continue on study at lower doses of causative agent. This study will use CTEP Common Terminology Criteria for Adverse Events (CTCAE) Version 4.0 for toxicity and adverse event reporting. A copy of the CTCAE version 4.0 can be downloaded from the CTEP home page (<http://ctep.info.nih.gov>). If toxicity cannot be clearly attributed to either agent alone, the toxicity will be attributed to both agents and modifications will be made to both agents. Should a patient require permanent discontinuation of either agent, the patient will come off protocol treatment.

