### 6.1. Dose modification for non-hematological toxicity

- Any Grade  $\geq 4$  non-hematological toxicity
- Any Grade 3 non-hematological toxicity with the exception of
  - Grade 3 nausea, vomiting, and or diarrhea that is controlled within 72 hours
  - Grade 3 elevations in ALT/AST that returns to meet initial eligibility criteria within 7 days of study drug interruption and do not recur upon study re-challenge.
  - Grade 3 Fever or infection  $< 5$  days duration
  - Grade 3 electrolyte imbalances that respond to oral or intravenous supplementation
  - Asymptomatic grade 3 creatinine kinase elevation, which remains  $< 10 \times \text{ULN}$ .
- Grade 2 non-hematological toxicity that persists for  $> 7$  days and considered intolerable to the patient and/or not controlled with standard supportive measurements.
- Any non-hematological toxicity requiring treatment interruption for  $> 21$  days. The exception would be grade 3 weight loss as it is unlikely that the patient would return to baseline within 21 days. Patients who experience Grade 3 weight loss may resume study medication with a dose reduction if the patient is deriving benefit from therapy, the weight loss has stabilized and treating physician feels it is in the best interest of the patient.

If a patient experiences a non-hematological toxicity requiring dose modification, the attributable treatment(s) will be held. If the toxicity resolves to meet study parameters within 21 days after discontinuation, the patient may resume treatment at reduced dose. (See Table in 6.3 below). Doses reduced for toxicity will not be re-escalated even if there is minimal or no toxicity with the reduced dose. Held doses will not be made up for and the cycle remains 28 days.

If toxicity does not meet parameters to restart within 21 days, then patient is removed from protocol therapy.

Two dose reductions will be allowed for toxicity. If a patient experiences toxicity requiring modification after two dose reductions, the patient must discontinue protocol therapy.

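### The Grade 3 pneumonitis row takes non-recovering patients off the study, where neighbouring rows and the follow-up sections imply off treatment only

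*Combined protocol and SAP*

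**What the plan says.** The protocol separates leaving therapy from leaving the study. Section 5.2 names both when it makes a new cycle conditional on the patient who "has not met one of the off protocol therapy or off study criteria". Section 5.5 lists the reasons for stopping protocol therapy, and toxicity is one of them. Section 5.7 deals with the other exit: "Patients will be removed from study when any of the criteria listed below applies". Its list is withdrawal of consent, death, loss to follow-up, and enrollment on another SARC treatment or long-term follow-up study.

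Section 5.6 sets out what follows when therapy stops early: "Patients who are removed from protocol therapy for a reason other than disease progression, should be followed up every 6 months by imaging". Survival contact comes later: "Once a patient experiences confirmed disease progression or starts a new anti-cancer therapy, the patient should be contacted by telephone every 6 months".

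The Grade 3 row of the pneumonitis table in Section 5.4.9 reads: "Patients will be withdrawn from the study if they fail to recover to ≤ Grade 1 within 2 weeks". The Grade 2 row of the same table reads: "Patients will be withdrawn from protocol treatment if they fail to recover to ≤ Grade 1 within 3 weeks". The Grade 4 row simply stops treatment.

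**The concern.** The Grade 3 row is an instruction, not background. It uses the language of study removal for an event that the neighbouring rows treat as a reason to stop drug. Taken literally, it gives an odd ordering: unresolved Grade 3 pneumonitis ends study participation, while the more severe Grade 4 event ends treatment and leaves the patient in Section 5.6 follow-up. The protocol gives no reason for this.

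What is at stake is follow-up for secondary outcomes. PFS and OS are secondary objectives (Section 1.2), and Section 13.4 analyses PFS by Kaplan-Meier. A patient taken off study for lung toxicity would be censored early, for a reason that may be related to prognosis.

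**Working it through.** No figure is in dispute, so the check compares the texts.

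1. **Same table.** Grade 2 without recovery: off protocol treatment (3-week limit). Grade 3 without recovery: off the study (2-week limit). Grade 4: treatment stopped. Only the Grade 3 row names the study.

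2. **General toxicity rules.** Section 6: "Should a patient require permanent discontinuation of either agent, the patient will come off protocol treatment". Section 6.1: "If toxicity does not meet parameters to restart within 21 days, then patient is removed from protocol therapy". Section 6.2 likewise ends protocol therapy if hematological toxicity again requires modification after two reductions. All of these use the treatment exit.

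3. **Off-study list.** None of the criteria in Section 5.7 is toxicity. The cross-reference in Section 5.2 does not help a site settle the matter. It points to 5.6 and 5.8, but 5.6 is follow-up, the relevant lists are in 5.5 and 5.7, and the contents list shows no 5.8.

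4. **What a literal reading removes.** The patient has not progressed and has started no new therapy, so Section 5.6 would call for six-monthly imaging. The survival calls would not yet have begun, because they start at progression or new therapy. An off-study patient would instead have the one-time Section 10.3 evaluations, and both kinds of later follow-up could be lost.

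5. **What it does not remove.** Section 5.6 ties adverse event follow-up to last treatment or to resolution or stabilization, not to study status. Section 7.2.1 requires reporting of Grade 3 or higher events to 30 days after the last dose. Sections 7.1.1.7 and 7.2.2 continue adverse event and SAE follow-up. The Grade 3 row itself repeats CT and lung function tests each cycle until baseline is regained.

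6. **Primary endpoint and design.** Treatment ends at the same time under either reading. Section 11.1.1 sets the best-response window in treatment cycles. If the four cycles of stable disease are counted in the same way, classification for the primary endpoint does not change. The two-stage figures in Section 13.1 reproduce from their own inputs: early termination under p0 = 0.95^7 = 0.698, and expected sample size = 7 + 14 × (1 − 0.698) = 11.2. Neither depends on off-treatment follow-up. The stopping rule in Section 13.5 counts Grade 4 or higher non-hematologic events, so this row does not enter it.

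7. **Scale.** One patient lost is 1/21 = 4.8% of the full sample, or 1/7 = 14.3% if the trial stops at stage 1. The documents give no rate for Grade 3 pneumonitis unresolved at 2 weeks.

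The comparison covers visible text only. The management algorithms in Sections 5.4.8, 5.4.10 and 5.4.11 are wholly or partly not shown.

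**The case against.** The strongest reply is that this is a slip that a reader of the whole protocol would correct. The column concerns sirolimus dose adjustment, and the sentence just before speaks of restarting protocol treatment. The protocol also uses the word study loosely elsewhere: Section 6 describes patients on reduced doses as remaining on study, and the contraception text in Section 3.1.14 speaks of discontinuing the study when the drug is evidently meant. This stands as evidence of intent, and it supports the correction. It does not make the sentence safe. The wording is mandatory and close to the trigger for the Section 10.3 evaluations, and with 10 to 15 centers planned (Section 12.3) a uniform reading cannot be assumed.

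It is also fair to say that a site consulting Sections 5.6 and 5.7 would probably keep the patient in follow-up, since 5.6 by its terms covers anyone off therapy without progression. And in earlier targeted-agent trials median time to progression was under 2 months (Section 2.1.3), so progression may often come first. Both points reduce the exposure.

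Four stronger readings are tempting and should not be drawn:

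- That Sections 6 and 6.1 are contradicted. They are not, strictly: a patient who leaves the study also leaves treatment. They show the protocol's usual practice. Nor does Section 5.7 say that its list is the only route off study. The real tension is with the neighbouring rows, with the absence of toxicity from 5.7, and with the imaging required by 5.6.
- That toxicity data would be lost. The provisions in step 5 of the working protect them.
- That the 2-week limit conflicts with the 21 days in Section 6.1. It can be read as a specific rule overriding a general one.
- That the number affected can be estimated from the sirolimus table in Section 7.3.2. That table places pneumonitis among less likely reactions (at least 3% but under 20%). The band covers a whole list of reactions, is not split by grade and concerns sirolimus alone. The share of cases that are Grade 3 and unresolved at 2 weeks would have to be invented, and it would drive the answer.

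**Conclusion.** The point stands as a minor wording inconsistency. The textual mismatch is clear; the consequence is remote. Follow-up is lost only if a patient has Grade 3 pneumonitis, fails to recover within 2 weeks, has not already progressed, and is treated at a site that reads the row literally. Only the secondary PFS and OS follow-up is exposed, in an unknown and probably very small number of patients. The conclusion assumes that the intent is withdrawal from treatment, which the surrounding text supports but does not state.

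**What to change.** In the Grade 3 row of the Section 5.4.9 table, replace *withdrawn from the study* with *withdrawn from protocol treatment and followed under 5.6*. Leave the 2-week limit unchanged.

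The cost is a few words in a protocol amendment. The follow-up is already required by Section 5.6, so no procedure is added and no clinical rule changes. It is best done prospectively, because missed imaging may not be recoverable.

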#### 5.4.10. Management of asymptomatic left ventricular ejection fraction (LVEF) reduction

Abbreviations: LVEF, Left ventricular ejection fraction; LLN, lower limits of normal

#### 5.4.11. Management of patients with visual symptoms or abnormal findings

Abbreviations: RPED, retinal pigment epithelial detachment; CSR; central serous retinopathy; RVO, retinal vein occlusion

## 5.5. Criteria for Removal off Protocol Therapy

Treatment may continue until one of the following criteria applies:

- Progressive Disease
  - Patients with radiographic or clinical evidence of disease progression following any treatment cycle will discontinue protocol therapy.
- Toxicity
  - Adverse events requiring removal from therapy.
  - Patient has not met parameter to start subsequent cycle.
- Administrative
  - Patient refusal of further treatments. Reasons must be noted on the patient's record.
  - If deemed in the best interest of the patient to be taken off protocol therapy, the Principal Investigator should be notified and the reasons for withdrawal noted in the patient's medical record.
  - Serious protocol violation as determined by the Principal Investigator
  -
- Another Medical
  - Development of any concurrent medical condition that precludes further administration of therapy.

## 5.6. Duration of Follow Up

Patients will be followed for adverse event(s) until 30 days after last treatment or until resolution or stabilization of the adverse event (whichever comes last). Patients who are removed from protocol therapy for a reason other than disease progression, should be followed up every 6 months by imaging to monitor disease status. Every effort should be made to collect information regarding disease status until the start of new anti-cancer therapy, disease progression, or death. Once a patient experiences confirmed disease progression or starts a new anti-cancer therapy, the patient should be contacted by telephone every 6 months to assess for survival status until death or withdrawal of consent or end of study, whichever occurs first.

## 5.7. Criteria for Removal from Study

Patients will be removed from study when any of the criteria listed below applies. The reason for study removal and the date the patient was removed must be documented in the Case Report Form including death or lost to follow up.

- Patient or guardian withdrawal of consent. Reasons must be noted on the patient's record.
- Death

- Lost to follow up
- Enrollment onto another SARC treatment study or SARC long term follow up study.

## 6. DOSING DELAYS / DOSE MODIFICATIONS

Patients who experience a toxicity requiring dose modification attributed to selumetinib and sirolimus but in the opinion of the investigator have benefited from the prior treatment cycle (decrease in size or stabilization of tumor or decrease in tumor related symptoms such as pain) may continue on study at lower doses of causative agent. This study will use CTEP Common Terminology Criteria for Adverse Events (CTCAE) Version 4.0 for toxicity and adverse event reporting. A copy of the CTCAE version 4.0 can be downloaded from the CTEP home page (<http://ctep.info.nih.gov>). If toxicity cannot be clearly attributed to either agent alone, the toxicity will be attributed to both agents and modifications will be made to both agents. Should a patient require permanent discontinuation of either agent, the patient will come off protocol treatment.

### 6.1. Dose modification for non-hematological toxicity

- Any Grade  $\geq 4$  non-hematological toxicity
- Any Grade 3 non-hematological toxicity with the exception of
  - Grade 3 nausea, vomiting, and or diarrhea that is controlled within 72 hours
  - Grade 3 elevations in ALT/AST that returns to meet initial eligibility criteria within 7 days of study drug interruption and do not recur upon study re-challenge.
  - Grade 3 Fever or infection  $< 5$  days duration
  - Grade 3 electrolyte imbalances that respond to oral or intravenous supplementation
  - Asymptomatic grade 3 creatinine kinase elevation, which remains  $< 10 \times \text{ULN}$ .
- Grade 2 non-hematological toxicity that persists for  $> 7$  days and considered intolerable to the patient and/or not controlled with standard supportive measurements.
- Any non-hematological toxicity requiring treatment interruption for  $> 21$  days. The exception would be grade 3 weight loss as it is unlikely that the patient would return to baseline within 21 days. Patients who experience Grade 3 weight loss may resume study medication with a dose reduction if the patient is deriving benefit from therapy, the weight loss has stabilized and treating physician feels it is in the best interest of the patient.

If a patient experiences a non-hematological toxicity requiring dose modification, the attributable treatment(s) will be held. If the toxicity resolves to meet study parameters within 21 days after discontinuation, the patient may resume treatment at reduced dose. (See Table in 6.3 below). Doses reduced for toxicity will not be re-escalated even if there is minimal or no toxicity with the reduced dose. Held doses will not be made up for and the cycle remains 28 days.

If toxicity does not meet parameters to restart within 21 days, then patient is removed from protocol therapy.

Two dose reductions will be allowed for toxicity. If a patient experiences toxicity requiring modification after two dose reductions, the patient must discontinue protocol therapy.

## 6.2. Dose modification for hematological toxicity

- Grade 4 thrombocytopenia
- Any hematological toxicity requiring treatment interruption for >21 days.

If a patient experiences a hematologic toxicity requiring dose modification, the attributable treatment(s) will be held. CBC should be checked twice weekly during this time. When toxicity resolves to meet study parameters within 21 days of discontinuation, the patient may resume treatment at the reduced doses (See Table in 6.3 below).

Two dose reductions will be allowed for toxicity. If a patient experiences hematological toxicity requiring dose modification after two dose reductions, the patient must discontinue protocol therapy.

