## **10.2. ON STUDY EVALUATIONS**

The following procedures will be performed during the treatment period:

Weekly During Cycle 1:

- History
- Physical exam: vital signs
- Hematology: complete blood count, differential. If patient has Grade 4 neutropenia or thrombocytopenia, then CBC should be checked every 3-4 days until recovery to Grade 3.

- Serum Chemistry: ALT, AST, alkaline phosphatase, bilirubin, BUN, creatinine, electrolytes, calcium, magnesium, phosphorus, total protein, albumin, serum creatinine phosphokinase.
- Patient diary
- Assessing of AEs

Cycle 1 Day 11 ± 3 days

- FDG-PET

Cycle 1 Day 15 (up to day 28)

- Serum Pharmacodynamic and Immune Markers: Mandatory blood samples for pharmacodynamics, genomics and immune infiltrates
- Tumor Biopsy: Optional serum/tissue samples for pharmacodynamics, genomics and immune infiltrates

Prior to Subsequent Cycles\*

- History
- Physical exam: vital signs, height, weight, body surface area
- Performance status: Lansky/Karnofsky (Appendix I)
- Hematology: complete blood count, differential. If patient has Grade 4 neutropenia or thrombocytopenia, then CBC should be checked every 3-4 days until recovery to Grade 3.
- Serum Chemistry: ALT, AST, alkaline phosphatase, bilirubin, BUN, creatinine, electrolytes, calcium, magnesium, phosphorus, total protein, albumin, serum creatinine phosphokinase.
- Fasting glucose and Fasting serum lipid profile (triglycerides, total cholesterol, HDL and LDL). Fasting = 12 hours prior to glucose testing and lipid testing
- Serum or urine pregnancy: required for females of childbearing potential.
- Patient diary
- Assessing of AEs

Prior to Cycles 3, 5, 7 and then every 3 cycles (within 7 days prior to start of subsequent cycle)

- ctDNA blood sample
- Radiologic imaging: Evaluation of other measurable or evaluable disease sites by appropriate radiological evaluation (i.e. CT scan, MRI)

Prior to Cycles 2, 3, 5, 9, 13, and then every 6 cycles

- Patient reported pain severity and pain interference assessments.

Prior to Cycles 6 and 12, and then every 6 cycles (within 14 days prior to start of subsequent cycle)

- Echocardiogram or Cardiac MRI and ECG
- Ophthalmology evaluation: Particular emphasis will be given to the evaluation of corneal opacifications and retinal changes.

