## STUDY CALENDAR

Studies to be obtained	Pre-treatment 	During Cycle 1	Prior to subsequent cycles	End of therapy
History and Physical with vitals	X	Weekly	X	X
Performance status (Karnofsky)	X		X	X
CBC, differential	X	Weekly 	X 	X 
Serum Chemistry 	X	Weekly	X	X
Fasting glucose and serum lipid profile 	X		X	X
Urine or serum pregnancy  test	X		X	
Echocardiogram or cardiac MRI and ECG	X 		Prior to cycles 6 and 12, and every 6 cycles	
FDG-PET	X 	Day 11 +/- 3 days		
Ophthalmology Exam	X		Prior to cycles 6 and 12 and every 6 cycles	
Tumor Evaluation (by CT, MRI)	X 		Prior to cycles 3,5,7 and then every 3 cycles	
Patient reported pain	X		Prior to cycles 2, 3, 5, 9, 13, and then every 6 cycles	
Patient Diary		Weekly	X	X
Pharmacodynamic/Immune Markers 	X	Day 15 (up to day 28) 	ctDNA only: prior to cycles 3, 5, 7 and then every 3 cycles	
Tumor biopsy 	X	Day 15 (up to day 28) 		
Genomic testing 	X	Day 15 (up to day 28) 		

 See Section 3.2

For patients who experience Grade 4 ANC or platelets, check CBC q 3-4 days until  $\geq$  Grade 3

Sodium, potassium, chloride, bicarbonate, calcium, phosphorus, magnesium, creatinine, glucose, blood urea nitrogen, total protein, SGOT (AST), SGPT (ALT), total bilirubin, alkaline phosphatase, uric acid.

Fasting = 12 hours prior to testing. Glucose and serum lipid panel (triglycerides, total cholesterol, HDL, LDL)

 For females of child-bearing potential

Can be done within 4 weeks prior to enrollment.

 For serum and/or tissue samples, See Section 2.5

 Tumor biopsy is optional and will be collected only for patients who provide written consent and has tumor accessible to percutaneous biopsy

 Baseline blood will be (mandatory) collected and for patients who provide written consent and has tumor accessible to percutaneous biopsy may be collected at baseline and day 15 per patient consent

 Will be collected during cycle 1 on any one day on or after day 15 (i.e. one day between day 15-28)

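### Section 6.2 requires no mid-cycle hold, and offers no workable dose reduction, for isolated Grade 4 neutropenia

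*Combined protocol and SAP*

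**What the plan says.** Section 6.2 names two hematological triggers: Grade 4 thrombocytopenia, and "Any hematological toxicity requiring treatment interruption for >21 days". The attributable drug is held only when a toxicity meets one of these. During the hold, CBCs are twice weekly, and the restart rule is: "When toxicity resolves to meet study parameters within 21 days of discontinuation, the patient may resume treatment at the reduced doses".

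Other sections that bear on Grade 4 neutropenia:

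- Section 10.2 says: "If patient has Grade 4 neutropenia or thrombocytopenia, then CBC should be checked every 3-4 days until recovery to Grade 3". Footnote 2 of the study calendar agrees: "For patients who experience Grade 4 ANC or platelets, check CBC q 3-4 days until" recovery. Neither mentions holding drug.
- Section 5.2, with 3.1.9, requires ANC to be at least 1000/µL again before each new cycle. It allows up to 21 days (to day 49) for recovery with no dose change, unless a modification criterion was met.
- Section 5.5 takes a patient off therapy if the cycle-start parameters are not met.
- Section 6.1 covers infection as a non-hematological toxicity: any Grade 4 or worse event counts, but "Grade 3 Fever or infection" lasting under 5 days is exempt. It has the same bullet about interruptions over 21 days, and adds: "If toxicity does not meet parameters to restart within 21 days, then patient is removed from protocol therapy".
- The stopping rule in 13.5 counts only non-hematologic events.

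**The concern.** The authors clearly had Grade 4 neutropenia in view, since 10.2 and the calendar name it beside Grade 4 thrombocytopenia. In 6.2 one of the pair brings a hold and a reduction, and the other brings nothing. A site that follows the text may keep a patient on full doses of a MEK inhibitor and an approved immunosuppressant while the neutrophil count stays at Grade 4, then restart at the same doses.

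The protocol's own background makes the event relevant:

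- Section 2.2.3 reports neutropenia as dose limiting in the phase 1 study whose MTD was selumetinib 50 mg BID with temsirolimus. That is the selumetinib dose used here.
- The same section puts neutropenia and anemia (20%) among the most common grade 3/4 events in the randomized combination arm, also at 50 mg BID.
- Section 2.2.2 lists neutropenia among the toxicities seen in at least 20% of patients on daily sirolimus alone (2 to 9 mg; grade not given).
- Section 7.3.2 lists febrile neutropenia and opportunistic infection risk for sirolimus.
- Section 3.1.6 sets no limit on prior chemotherapy regimens.

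The exposure is mainly in cycle 1, when CBCs are weekly. Later scheduled CBCs fall just before each cycle, where the ANC gate acts at once.

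**Working it through.** The plan states no figure to reproduce. The check is one of logic, followed by a count of the doses the text permits.

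**Step 1. What each event requires mid-cycle.**

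| Event | Required step | Restart dose |
|---|---|---|
| Grade 4 thrombocytopenia (6.2) | Hold, CBC twice weekly | Reduced, if recovered within 21 days |
| Grade 3 or worse rash (5.4.5) | Interrupt both drugs | Reduced, once Grade 2 or less |
| Isolated Grade 4 neutropenia (6.2, 10.2, 5.2) | CBC every 3-4 days only | Unmodified, if the ANC gate is met within 21 days |

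**Step 2. Can the second trigger in 6.2 give a reduction?** Let D be the length in days of the interruption that the toxicity requires. The trigger needs D > 21. Restart at a reduced dose needs D ≤ 21. No value of D satisfies both, so the bullet cannot lead to a reduced-dose restart for any hematological toxicity. It also presupposes an interruption, and no rule requires one mid-cycle for neutropenia. A delay at cycle start ends at day 28 + 21 = 49 under 5.2, after which 5.5 applies. The general statement in section 6, that benefiting patients "may continue on study at lower doses of causative agent", applies to toxicities that already require modification, so it does not fill the gap.

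**Step 3. Exposure the text permits.** Assume a weekly cycle 1 CBC on day 8 shows Grade 4 neutropenia that lasts to day 28, without a qualifying infection.

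- Days 8 to 28 inclusive: 28 − 8 + 1 = 21 days.
- Selumetinib 50 mg BID: 21 × 2 = 42 doses.
- Sirolimus 4 mg once daily: 21 × 1 = 21 doses.
- Repeat CBCs every 3 days: days 11, 14, 17, 20, 23, 26, which is 6. Every 4 days: days 12, 16, 20, 24, 28, which is 5.

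All 5 or 6 repeat counts could show Grade 4 with no required action on drug. This is a maximum, not an expected course.

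**Step 4. Frequency.** The only related rate is the 20% in 2.2.3: 0.20 × 35 = 7 patients. The text does not say whether 20% applies to each event or to both together, and does not separate Grade 4 from Grade 3. The number affected in this trial cannot be derived from it.

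**The case against.** The omission may be deliberate. Close counting with an ANC gate before the next cycle is a coherent policy, and parts of the protocol fit it. Thrombocytopenia is listed at 30% for sirolimus in 7.3.2, while leukopenia and febrile neutropenia are in the less likely group. Neutropenia is absent from the selumetinib list in 7.3.1 (N = 355). The selumetinib-alone phase 1 study in 2.2.1.2 had one Grade 4 event, hypoglycemia. This supports a low rate and argues against compulsory reduction after a brief event. It does not explain why a hold should be required for platelets and not for neutrophils.

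Other safeguards exist. Grade 3 or worse events are reported (7.2.1), adverse events are reviewed at least monthly (13.5), 5.5 allows removal in the patient's best interest, and the research monitor may remove patients (12.2). Many investigators would hold drug anyway. A reader might therefore go too far and infer that neutropenia is uncontrolled; the documents do not support that. But these controls are discretionary or act after the event, and with 10-15 centers (12.3) they do not make a common hold rule.

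A reader might also infer that 6.2 contradicts itself over 21 days. It does not give opposite instructions. The bullet is inert: read with the identical bullet and removal sentence in 6.1, and with 5.5, it points to removal.

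Finally, a reader might multiply 20% by 21 and expect about four affected patients (0.20 × 21 = 4.2). The documents do not support that number. It would treat every grade 3/4 event as Grade 4 neutropenia, and carry a rate from weekly intravenous temsirolimus to daily oral sirolimus.

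**Conclusion.** The gap is real and should be fixed. As written, isolated Grade 4 neutropenia found mid-cycle requires only repeat CBCs until the next cycle's ANC gate or a qualifying infection under 6.1. No workable route leads to a reduced dose. The permitted exposure is at most 42 selumetinib and 21 sirolimus doses for an event found on day 8 of cycle 1. That assumes the count stays at Grade 4 to day 28 and the investigator does not hold on judgement.

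Confidence is high on the wording. It is lower on clinical impact, because the Grade 4 neutropenia rate is not given and may be low. The primary endpoint, sample size and decision rule are not affected; this is a patient-safety point. The 21-day bullet is a secondary matter of tidying.

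**What to change.** 1. Add Grade 4 neutropenia to the 6.2 triggers. Hold the attributable drug or drugs, check CBC twice weekly as 6.2 already provides, and restart once ANC is at least 1000/µL within 21 days. After a brief first event, restart at the same dose. If the event is prolonged or recurs, restart at the 6.3 reduced dose. The medical team should set the duration that counts as prolonged.
2. Replace the bullet on interruptions over 21 days in 6.2 with the removal sentence from 6.1, which agrees with 5.5.
3. State whether this rule from 6.1 also governs 6.2: "Doses reduced for toxicity will not be re-escalated even if there is minimal or no toxicity with the reduced dose".

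These are wording changes with no new scheduled tests, because the weekly, every 3-4 day and twice-weekly CBCs are already in the protocol. The real cost is dose intensity, in a disease where 2.1.3 reports a median time to progression under 2 months. A 7-day hold drops 7 × 2 = 14 selumetinib doses and 7 sirolimus doses, or 7/28 = 25% of a cycle. A first reduction cuts selumetinib by (50 − 35)/50 = 30% and sirolimus by (4 − 3)/4 = 25%, permanently if the no-re-escalation rule applies. Keeping the reduction for prolonged or recurrent events limits that larger cost to the patients who need it.
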